The quality of life as assessed by ANCOVA analysis of the KCCQ summary score for complete 2-year data showed an improvement of 7.8 ± 2.3 points for the device arm compared to decline of 12.1 ± 2.3 points for the control arm. Similarly, 6MWD outcomes showed a decline of 55 ± 10.8 points for the device arm vs decline of 93.5 ± 10.9 for the control arm. Adverse event rates were consistently low and strongly in favor of the device arm. Overall, the data concluded that at 36 months transcatheter mitral leaflet approximation with the MitraClip was safe, provided durable reduction in MR, reduced the rate of HF hospitalizations, and improved survival, QOL and functional capacity compared to GDMT alone.

Based on this clinical evidence clinical benefit of MitraClip System continues to demonstrate significant benefit to MR patients and is suitable for use in the study for safety and efficacy in the Russian population.

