2.2.4 Summary of Previous Clinical Studies

This section summarizes results of relevant studies of the MitraClip NT System Clinical Program. Please refer to the Investigator Brochure for a summary of the clinical investigations sponsored by Abbott and all published data on the MitraClip therapy in addition to the relevant previous clinical experience with medical devices that have similar characteristics, and the history of adverse device effects.

Rationale for the MitraClip NT System Russian Trial is subsequently presented in the context of this scientific body of evidence.

EVEREST I Design and Results

The EVEREST I Feasibility trial was the first prospective, multi-center, non-randomized trial to evaluate the preliminary safety and effectiveness of the percutaneous **MitraClip** System in patients with moderate-to-severe (3+) or severe (4+) MR in surgical candidates. After undergoing the **MitraClip** procedure, patients were followed at discharge, 30 days, 6, 12, 18 and 24 months and every year thereafter through 5 years. An independent Echocardiography Core Laboratory (ECL) assessed MR severity and other echocardiographic parameters at baseline and follow-up. The last patient has completed 5-year follow-up and the study is now closed.

A total of 55 patients were enrolled in the trial. The **MitraClip** device was implanted in 89% of patients and the trial met its pre-specified safety acceptance criterion, demonstrating mechanistic feasibility of implant and safety of the **MitraClip** System and procedure. There were no intra-procedural deaths. The procedure time averaged approximately 4 hours, patients were hemodynamically stable during the procedure, and the average length of hospital stay was approximately 3 days. A majority of patients (70.9%) experienced reduction in MR severity to 2+ or less at discharge. No **MitraClip** device embolizations occurred in this cohort. The rate of single leaflet device attachment (SLDA) in this initial cohort of patients treated was 10.2%. A majority of SLDAs were detected early (within 30 days post- **MitraClip** procedure). Patients demonstrated

Abbott

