improvement in NYHA Functional Class and left ventricular measurements that were sustained through 5 years. At 5 years, freedom from death was 86.4% and freedom from mitral valve surgery was 55.1%. The results of the EVEREST I trial at 5 years provide evidence of the safety and long-term durability of the **MitraClip** device in the early cohort of patients treated in the United States.

EVEREST II Randomized Controlled Trial (RCT) Design and Results

The EVEREST II RCT is a prospective, multi-center, randomized controlled trial in which patients with moderate-to-severe (3+) or severe (4+) MR were randomized in a 2:1 ratio between the Device group (**MitraClip** device) and the Control group (mitral valve surgery). Patient follow-up occurred at discharge, 30 days, 6, 12, 18 and 24 months and yearly thereafter through 5 years. An independent Echocardiography Core Laboratory (ECL) assessed MR severity and other echocardiographic parameters at baseline and follow-up. The trial was intended to demonstrate superiority of safety balanced against reduced effectiveness of the **MitraClip** device when compared to mitral valve surgery. All patients have completed 5 years of follow-up and the study is now closed.

The trial enrolled 279 patients: 184 in the Device group and 95 in the Control group. Of these, 178 patients in the Device group underwent the **MitraClip** procedure and 80 patients in the Control group underwent mitral valve surgery. The trial met both primary safety and effectiveness endpoints. There were no intra-procedural deaths. Among patients who underwent the **MitraClip** procedure in the Device group (**MitraClip** patients), a device was implanted in 89% of patients. The procedure time averaged approximately 3 hours, patients were hemodynamically stable during the procedure, and the average length of hospital stay was less than 3 days. In comparison, the average length of hospital stay for patients undergoing surgery in the Control group (surgery patients) was days. A large majority (94.9%) of **MitraClip** patients were discharged home without home healthcare. In comparison, 71.3% of surgery patients were discharged home without home healthcare. A majority of **MitraClip** device patients (77%) experienced reduction in MR severity to 2+ or less at discharge, while 100% of patients undergoing mitral valve surgery in the Control group experienced reduction in MR severity to 2+ or less.

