Patients who underwent the **MitraClip** procedure experienced a 30-day major adverse event rate (composite of death, myocardial infarction (MI), re-operation for failed surgical repair or replacement, non-elective cardiovascular surgery for adverse events, stroke, renal failure, deep wound infection, ventilation for greater than 48 hours, GI complication requiring surgery, new onset of permanent atrial fibrillation, septicemia and major bleeding complication) of 7.9% versus 50% in patients who underwent mitral valve surgery in the Control group. Excluding the most common event of major bleeding complication, **MitraClip** device patients still experienced a lower major adverse event rate (4.5%) than surgery patients (11.3%) ($p=0.057$).

Through 30 days, **MitraClip** patients experienced a lower site-reported adverse event rate than surgery patients in the following categories: cardiac rhythm disorders (atrial arrhythmias, bradycardia, ventricular arrhythmia), congestive heart failure, peripheral edema, anemia, infections, neurologic events and respiratory events. At 30 days, **MitraClip** patients experienced a higher event rate than surgery patients in the following categories: atrial septal defect, myocardial ischemia, residual or recurrent MR, single leaflet device attachment (SLDA), gastrointestinal bleed, and vascular complications such as hematoma, bleed or bruising. Beyond 30 days through 5 years, site-reported adverse events occurred at a low rate in both **MitraClip** and surgery patients and there was no signal for an elevated adverse event rate in either group.

Abbott

Through 5 years, there was only one confirmed case of mitral stenosis (0.6%) reported in patients implanted with the **MitraClip** device. Through 5 years, no **MitraClip** device embolizations have occurred. SLDAs occurred at a lower rate (6.3%) than that observed in the EVEREST I trial (10.2%). A majority of the SLDAs were detected early (within 30 days post- **MitraClip** procedure).

There was no difference in mortality rates between patients treated in either group during the entire 5-year follow-up period. Freedom from mortality at 12 months, 24 months, 3 years, 4 years and 5 years was 93.7%, 90.0%, 87.5%, 83.4% and 81.2% respectively in **MitraClip** patients, and 92.3%, 89.6%, 85.3%, 82.3%, and 79.0%, respectively in surgery patients.

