5.4.1 Subject Registration

A subject is considered registered when after enrolment and screening procedures it has been confirmed that the subject meets all inclusion criteria and none of the exclusion criteria and upon femoral vein puncture for transseptal access in preparation for the **MitraClip NT System** insertion.

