#### 2.3.2 Descriptive Endpoints

The analyses for the descriptive endpoints will be performed using the methods described in Section 2.2 for ATP populations.

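### The only analysis set includes subjects who never receive a clip, so post-procedure gradient and valve area, and by default clip-dependent complication rates, are diluted whenever an implant fails

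*Protocol*

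**What the plan says.** SAP 2.1.1 defines a single population, the ATP: eligible subjects registered into the study. Protocol 5.4.1 places registration "upon femoral vein puncture for transseptal access in preparation for the" system's insertion, so a subject counts before any clip has been placed. SAP 2.3.1 uses the ATP for the primary endpoint, and SAP 2.3.2 extends it: "The analyses for the descriptive endpoints will be performed using the methods described in Section 2.2 for ATP populations".

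The descriptive endpoints in SAP 1.4.2 include mean mitral valve pressure gradient (MVG) and mitral valve area (MVA) at baseline, discharge, 10 days and 30 days. Protocol 6.1 follows subjects on this schedule whether or not a clip was implanted.

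Single leaflet device attachment (SLDA), embolization and mitral stenosis appear as components of Device Success. Clip thrombosis and erosion or migration appear only among the anticipated events in Protocol section 7, Table 5. For adverse events, SAP 2.2.2 promises counts and percentages but names no denominator.

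Protocol 2.2.4 cites earlier SLDA rates. For EVEREST I: "The rate of single leaflet device attachment (SLDA) in this initial cohort of patients treated was 10.2"%. For the EVEREST II randomized trial: "SLDAs occurred at a lower rate (6.3%) than that observed in the EVEREST I trial (10.2"%). For the High Risk Registry the figure is 1.3%.

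**The concern.** A subject without a clip cannot have SLDA, clip embolization, clip thrombosis, clip migration or clip-induced stenosis. Counting such subjects in the denominator means that the more implants fail, the lower the reported complication percentage. The same holds for MVG: without a clip there is no clip effect on the gradient, yet the value enters the post-procedure mean. For MVA the pull is in the opposite direction, toward the larger pre-procedure area.

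For success endpoints the ATP is the cautious choice, because a failed implant counts as a failure. For harms that need an implant it works the other way. Safety is a stated objective (Protocol 2.1, SAP 1.2), and the SLDA rates a reader would naturally look to are, in at least two studies, on another base.

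**Working it through.** **1. Base of the cited SLDA rates** (inputs from Protocol 2.2.4; rates taken as simple proportions).

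EVEREST I: "A total of 55 patients were enrolled in the trial", and the "device was implanted in 89% of patients and the trial met its pre-specified safety acceptance criterion".
- Counts out of 55 that round to 89%: 0.885 × 55 = 48.7 to 0.895 × 55 = 49.2, so only 49.
- Reproducing 10.2%: 5/49 = 10.20%. Out of 55, 5/55 = 9.1% and 6/55 = 10.9%; no count gives 10.2%.
- The same paragraph's 70.9% with MR 2+ or less at discharge is 39/55, so the section mixes bases without saying so.

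EVEREST II randomized trial: "Of these, 178 patients in the Device group underwent the" procedure, and "a device was implanted in 89% of patients".
- 0.885 × 178 = 157.5 to 0.895 × 178 = 159.3, so 158 or 159 were implanted.
- Reproducing 6.3%: 10/158 = 6.33% or 10/159 = 6.29%. Out of 178, 11/178 = 6.2% and 12/178 = 6.7%. Out of the 184 randomized to device, 6.25% to 6.35% is 11.5 to 11.7, which contains no whole number.

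High Risk Registry: 78 enrolled, 96.2% implanted, so 75. The 1.3% fits both 1/75 = 1.33% and 1/78 = 1.28%. The base cannot be determined.

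**2. Event rates in this trial** (n = 16, Protocol 5.7; assuming the cited implant rates carry over).

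With x events and I subjects implanted, the per-attempt rate x/16 equals the per-implant rate x/I multiplied by I/16. The expected relative reduction is 1 minus the implant rate: 1 − 0.89 = 11%, or 1 − 0.962 = 3.8%.

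- Chance that all 16 are implanted, so that there is no difference: 0.89^16 = 0.15; 0.962^16 = 0.54.
- Expected number implanted: 16 × 0.89 = 14.2; 16 × 0.962 = 15.4.

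| Subjects with SLDA | Per attempt (16) | 15 implanted | 14 implanted |
|---|---|---|---|
| 1 | 6.3% (0.2 to 30.2) | 6.7% (0.2 to 31.9) | 7.1% (0.2 to 33.9) |
| 2 | 12.5% (1.6 to 38.3) | 13.3% (1.7 to 40.5) | 14.3% (1.8 to 42.8) |

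Brackets are exact Clopper-Pearson 95% intervals. One event moves by 0.4 to 0.9 percentage points, against an interval 30.2 − 0.2 = 30 points wide.

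**3. Gradient and valve area.** With 14 of 16 implanted, the ATP mean at a visit is (14 × implanted mean + 2 × mean without clip)/16. It differs from the implanted mean by 2/16 = one eighth of the gap between the two groups. The documents give no gradient values, so this cannot be put in mmHg. The implanted mean also cannot be recovered from the ATP mean without individual data.

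**The case against.** The strongest reply is that the ATP denominator for individual complications is an inference. SAP 2.3.2 governs the listed endpoints, none of these complications is a stand-alone endpoint, and SAP 2.2.2 refers to table mock-ups that are not in the documents and may settle the matter. That stands: for events, the most that can be said is that no other denominator is named.

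A reader might infer that the plan flatters the device on safety and that its results cannot be set against the earlier studies. The documents do not support that.
- Where SLDA enters an endpoint, Device Success, a subject without a clip is already a failure.
- Event counts and the Implant Rate are reported on the same 16 subjects, so a per-implant event rate can be derived. The earlier rates convert too: 5/55 = 9.1% and 10/178 = 5.6%.
- No hypothesis test is planned (Protocol 8.3), and neither document plans a comparison with the earlier trials.
- A per-attempt rate is a proper quantity: the risk to a patient taken to the procedure.

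A reader might also infer that all the cited SLDA rates are per implanted patient; the High Risk Registry figure fits either base.

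On gradient, it is fair to say that values in subjects without a clip need not stay unchanged, since Table 5 lists mitral valve injury and chordal rupture, and that the SAP specifies visit summaries rather than an analysis of change. This limits any claim about the amount of dilution. It does not answer the main point: MVG and MVA are listed endpoints, SAP 2.3.2 puts them on the ATP, and a pooled mean cannot be converted afterwards.

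**Conclusion.** The point holds as a modest gap in the analysis sets. It is firmest for MVG and MVA, where the ATP applies expressly. For clip-dependent events the ATP is the default because nothing else is named.

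The expected relative lowering of event rates is 3.8% to 11%, assuming implant rates of 96.2% to 89% carry over to this trial. It is zero if every subject receives a clip, and it is minor beside the uncertainty at n = 16. The mismatch with the cited evidence is established for EVEREST I and the EVEREST II randomized trial only, and it is a difference of base, not a bar to comparison. The ATP remains right for the primary endpoint and the success rates. What justifies acting is that the change costs almost nothing and stops failed implants from improving the reported clip safety figures.

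**What to change.** - In SAP 2.1, add an Implanted Population: ATP subjects with at least one clip deployed.
- Report SLDA, clip embolization, clip thrombosis, erosion or migration, mitral stenosis, and post-procedure MVG and MVA on that population beside the ATP, and state the denominator of each percentage.
- Keep the ATP for the primary endpoint, success rates and everything else.
- In Protocol 2.2.4, state the implanted base for the EVEREST I and EVEREST II randomized trial SLDA rates only. Leave the High Risk Registry rate unlabelled unless its source settles the base.

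Cost: a few sentences and one extra column in the device-complication and MVG/MVA tables. The implanted column will show slightly less favourable clip complication figures if any implant fails.

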2.2.5 Description of the Control Devices

N/A.

Abbott

2.2.6 Device Handling

The Sponsor requires the clinical site to store all investigational products according to the labeling and Instructions for Use in a secure area to prevent unauthorized access or use.

3.0 CLINICAL INVESTIGATION DESIGN

3.1 Clinical Investigation Procedures and Follow-up Schedule

The Flow Chart and the Follow-up requirements of this clinical investigation are described below.

Figure 10: Clinical Investigation Flow Chart

Overall Flow of the Trial and Follow-up Schedule

[figure not shown]

Figure 10 – Flow-chart

3.2 Early Termination or Suspension of the Clinical Investigation

Abbott

While no formal statistical rule for early termination of the clinical investigation for insufficient effectiveness of the device under investigation is defined, the Sponsor reserves the right to discontinue the clinical investigation at any stage or reduce the follow-up period with suitable written notice to the investigator. Possible reason(s) may include, but are not limited to:

- Unanticipated adverse device effect (e.g., UADE) occurs and it presents an unreasonable risk to the participating subjects
- An oversight committee (e.g., Steering/Executive Committee, Data Monitoring Committee) makes a recommendation to stop or terminate the clinical investigation (such as higher frequency of anticipated adverse device effects)
- Further product development is cancelled.

Should the clinical investigation be discontinued by the Sponsor, subjects will be followed per routine hospital practice with device-related AEs reported to the Sponsor as per vigilance/commercial reporting requirements. The investigator shall return all clinical investigation materials (including devices) to the Sponsor, and provide a written statement to the IRB/EC (if applicable). All applicable clinical investigation documents shall be subject to the same retention policy as detailed in Section 11.5 of the CIP.

A Principal Investigator, IRB/EC or regulatory authority may suspend or prematurely terminate participation in the clinical investigation at the investigational site(s) for which they are responsible. The investigators will follow the requirements specified in the Clinical Trial Agreement.

If the Sponsor suspends or prematurely terminates the clinical investigation at an individual site in the interest of safety, the Sponsor will inform all other Principal Investigators.

If suspension or premature termination occurs, the Sponsor will remain responsible for providing resources to fulfill the obligations from the CIP and existing agreements for following the subjects enrolled in the clinical investigation, and the Principal Investigator or authorized designee will promptly inform the enrolled subjects at his/her site, if appropriate.

If suspension or premature termination occurs, the Principal Investigator or authorized designee will promptly inform the enrolled subjects at his/her site, if appropriate, and return patients to their standard medical treatment.

4.0 ENDPOINTS

4.1 Primary Endpoint

Successful implantation of the MitraClip NT device resulting in a decrease in the MR severity grade as assessed from the discharge echocardiogram (10-day echocardiogram will be used if discharge is unavailable or uninterpretable). Subjects who die or undergo mitral valve surgery before discharge will be considered a failure for the procedure.

Abbott

4.2 Descriptive Endpoints

Clinical Endpoints:

- Technical Success: Alive with successful access, delivery and retrieval of the device delivery system, and deployment and correct positioning of a Clip, and no need for additional unplanned or emergency surgery or re-intervention related to the device or access procedure
- Device Success at 30-day post-procedure: Alive with original intended Clip(s) in place, and no additional surgical or interventional procedures related to access or device since completion of the original procedure, and intended performance of the Clip(s) with MR reduction to \leq mild and freedom from device related Serious Adverse Events (SAE)s (i.e. embolization, mitral stenosis, single leaflet device attachment, iatrogenic atrial septal defect, myocardial perforation, or the need for mitral valve replacement instead of repair due at least in part to the MitraClip procedure or the presence of the MitraClip NT device)
- Procedural Success at 30-day post-procedure: No procedure related SAEs (i.e. death, stroke, MI, renal failure, and non-elective cardiovascular surgery for device or procedure related adverse events occurring after the attempted MitraClip procedure (i.e. femoral vein puncture for trans-septal access)
- All-cause mortality
- Number of hospitalizations and reason for hospitalization (i.e. heart failure, cardiovascular, non-cardiovascular) through follow up
- Major bleeding requiring transfusion through follow up
- Six Minute Walk Test (6MWT) distance at baseline, 10 days and 30 days
- Average doses of concomitant cardiac medications at baseline, procedure, 10 days and 30 days
- NYHA will be done on screening day, 10 days, 30 days

Device and Procedure-Related Endpoints:

- Implant Rate: Defined as the rate of successful delivery and deployment of one or more MitraClip NT devices with echocardiographic evidence of leaflet approximation and retrieval of the delivery catheter
- Device Procedure Time: Defined as the time elapsed from the puncture of the groin for the trans-septal procedure to the time the Steerable Guide Catheter is removed
- Total Procedure Time: Defined as the time elapsed from the first of intravascular catheter placement, or transesophageal echocardiogram (TEE), to the removal of the last catheter and TEE
- Device Time: Defined as the time the Steerable Guide Catheter is placed in the intra-atrial septum until the time the MitraClip NT (CDS) is retracted into the Steerable Guide Catheter
- Fluoroscopy duration: Defined as the duration of exposure to fluoroscopy during the MitraClip NT procedure
- Length of stay in Intensive Care Unit/Critical Care Unit/Post-Anesthesia Care Unit (ICU/CCU/PACU)
- Length of hospital stay excluding rehabilitation stay
- Length of rehabilitation stay
- Location to which subject was discharged (home or another facility)
- If subject discharged to another facility, length of stay at facility to which subject was discharged
- Mitral valve surgery (including type of surgery), including reason for intervention

Abbott

- Additional MitraClip NT device intervention, including reason for intervention

Echocardiographic Endpoints:

The following echocardiographic endpoints will be reported at baseline, discharge, 10 days, 30 days. Echocardiographic endpoints will be assessed at baseline, discharge, 10 days, 30 days.

- MR Severity Grade
- Effective Regurgitant Orifice Area
- Regurgitant Volume (RV)
- Regurgitant Fraction (RF)
- Left Ventricular End Diastolic Volume (LVEDV)
- Left Ventricular End Systolic Volume (LVESV)
- Left Ventricular End Diastolic Dimension (LVEDD)
- Left Ventricular End Systolic Dimension (LVESD)
- Left Ventricular Ejection Fraction (LVEF)
- Right Ventricular Systolic Pressure (RVSP)
- Mitral Valve Area (MVA)
- Mean Mitral Valve Pressure Gradient (MVG)
- Systolic Anterior Motion of the mitral valve (present or absent)
- Forward Stroke Volume (FSV)
- Cardiac Output (CO)
- Cardiac Index (CI)

